PROJECT TITLE:

Web-MAP for children with chronic pancreatitis (WebMAP- CP)

PRINCIPAL INVESTIGATOR:

Name: [name]
Department: Child Health, Behavior and Development
[contact]
Email Address: [contact]

Contents

1.	Objectives.....	4
2.	Background.....	4
3.	Study Endpoints	7
4.	Drugs, Devices and Biologics	7
5.	Procedures Involved	7
6.	Data and Specimen Banking	9
7.	Sharing of Results	10
8.	Study Timelines	10
9.	Study Population	10
10.	Number of Subjects	11
11.	Withdrawal of Subjects	11
12.	Risks to Subjects.....	12
13.	Potential Benefits to Subjects	13
14.	Data Analysis/Management	13
15.	Confidentiality	14
16.	Provisions to Monitor Data to Ensure the Safety of Subjects	15
17.	Use of Social Media	16
18.	Research Related Injury.....	16
19.	Recruitment Methods	16
20.	Consent/Assent Process	17
21.	Process to Document Consent in Writing	19
22.	HIPAA Authorization and RCW Criteria	20
23.	Payments/Costs to Subjects	21
24.	Setting.....	21
25.	Resources Available.....	21
26.	Coordinating Center Procedures	22
27.	Good Clinical Practice.....	22

1. Objectives

1.1. Purpose, specific aims, or objectives:

This project will deliver a first ever randomized, double-blinded and placebo controlled nonpharmacological pain intervention to children with CP/ARP and potentially identify patient-specific biological and psychosocial factors associated with favorable versus poor responsiveness to CBT to enable precision medicine approaches, consistent with priorities of the Federal Pain Research Strategy.

Aim 1. To determine the efficacy of web-based CBT in children with CP/ARP.

Aim 2. To identify the genetic co-variants associated with treatment response to web-based CBT.

Aim 3. To identify clinical and psychosocial factors associated with treatment benefit from web-based CBT.

1.2. Hypotheses to be tested:

Hypothesis 1: Children receiving CBT will have greater reductions in pain-related disability (primary outcome), pain, anxiety and depressive symptoms, opioid use, and HRQOL (secondary outcomes) compared to the education control group. To test this hypothesis, we will conduct a randomized and double-blinded controlled trial of web-based CBT (WebMAP) vs education (WebED). We will evaluate changes in pain, HRQOL, emotional functioning, medication use, health care utilization at baseline, 2 months, and 6 months.

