Hypothesis 2: Genetic co-variants associated with pancreatitis, inflammation, lipid and drug metabolism will predict response to therapy. To test this hypothesis, we will evaluate targeted next generation sequencing of genes involved in pancreatitis risk (CASR, CFTR, CTSC, SBD5, SBDSP – pseudogene, SPINK1, CEL, CELP – pseudogene, CPA1, CLDN1 (key SNPs), PRSS1, PRSS2, PRSS3, PRSS1-2 locus, GGT1 and UBR1)), lipid metabolism (APOA5, APOC2, FABP, LPL), inflammation (IL10, IL22, IL22RA1, IL22RA2, IL23R) and drug metabolism (COMT, HTR2A, CYP2C19, CYP2D6, CYP3A4, CYP3A5, OPRD1 and OPRM1) in children with CP/ARP who undergo WebMAP vs WebED. Risk stratification analysis will be done to identify genotypic factors that will predict response to treatment.

Hypothesis 3: Baseline clinical characteristics (i.e. demographics, age at diagnosis, abdominal pain frequency and severity, number of pancreatitis attacks, imaging findings), and baseline emotional and family functioning will predict pain and health outcomes at 6 months.

2. Background

2.1. Relevant prior experience and gaps in current knowledge:

Current state of the science: pediatric pain self-management interventions. Psychological treatments for pediatric chronic pain have included predominantly cognitive-behavioral therapy (CBT) self-management interventions such as pain education, relaxation training, cognitive skills, behavioral activation, and relapse prevention. Psychological therapies are effective in reducing pain intensity and pain-related disability of children and adolescents with chronic pain, including abdominal pain 15. To date, there are no established pediatric pain self-management interventions for pediatric CP/ARP.

Challenges to provide pain self-management interventions. Despite the effectiveness of pain self-management programs, many barriers prevent children from receiving self-management for chronic pain: i) children/caregivers may be reluctant to seek out mental health services for pain management, ii) access may be limited due to geographic restrictions (e.g., available only in tertiary centers), iii) small number of trained clinicians are available to deliver the therapies, iv) families often experience burden in taking time off school and work, and v) direct and indirect costs of therapy visits are often prohibitive. Highly trained personnel deliver

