
Blood draw and collection will be done by the INSPPIRE 2 study, but will not be done for patients recruited from community organizations who are not participating in INSPPIRE 2. The data we need will be pulled from that study for analysis. LMM will be our primary analytic tool to investigate the association between genetic co-variants and treatment response in internet-based CBT. In the LMM, repeated measures of painrelated disability will be used as the dependent variable. The covariates include time, gene and demographic variables (e.g., sex) when necessary. In the initial evaluation, "genetic signatures" will be used as covariates. This approach markedly reduces complexity by combining known pathogenic variants in a class into an object such as "CFTR-related disorders", "Pathologic Trypsins", "Unfolded protein response (UPR)", "Lipotoxicity", "idiopathic" and "others" for etiology, as well as "opiate pharmacogenetics defect", "pain receptor" and others for modifiers. In addition, pathogenic variants with large effects (e.g. PRSS1 p.R122H, SPINK1 p.N34S) or high frequency (e.g. CTRC g.60G haplotype) will be evaluated as independent covariates. To investigate multiple genes and genetic signatures, we will conduct univariate gene analysis by regressing each gene independently on the pain-related disability outcome to see if there is reasonable signal of association between the gene and pain-related disability. Using this procedure, we screen out the genes with p value > 0.1. We then build

a multivariate model based on the genes with p value < 0.1 in the univariate analysis. In the case that the number of genes included in the multivariate model is still large, model selection (e.g., using LASSO) will be performed to obtain a parsimonious model and identify the genes that are significantly associated with the outcome pain-related disability. Further analysis utilizing machine learning programs for cluster analysis, such as principle component analysis, will be conducted as complementary and confirmatory analyses.

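### The Aim 2 genetic analysis names no treatment-response term, so its gene effect cannot separate genes that mark severity from genes that predict response to CBT

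*Combined protocol and SAP*

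**What the plan says.** Section 1.1 gives Aim 2 as "To identify the genetic co-variants associated with treatment response to web-based CBT". Hypothesis 2 in section 1.2 studies the genes "in children with CP/ARP who undergo WebMAP vs WebED" and adds: "Risk stratification analysis will be done to identify genotypic factors that will predict response to treatment". No model for that stratification appears anywhere.

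The analysis is in section 14.1. Its stated purpose is treatment response, and "repeated measures of painrelated disability will be used as the dependent variable". Then: "The covariates include time, gene and demographic variables (e.g., sex) when necessary". Each gene is regressed singly on the disability outcome "to see if there is reasonable signal of association between the gene and pain-related disability". The next step is "Using this procedure, we screen out the genes with p value > 0.1". The multivariate model, with LASSO if many genes remain, is to "identify the genes that are significantly associated with the outcome pain-related disability".

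The Aim 1 mixed model, earlier in 14.1, does name time, intervention condition and their interaction. The only covariates that 14.1 requires in every model are age and sex. The Aims 2 and 3 power statement in 10.4 is for a correlation of 0.27 between gene (or a baseline characteristic) and pain-related disability, with 112 subjects.

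**The concern.** Response to CBT is a difference in treatment effect between carriers and non-carriers. In a two-arm trial with repeated measures, that is a gene-by-arm effect on follow-up adjusted for baseline, or a gene-by-arm-by-time effect. The listed terms contain neither. Disability is measured at T1, T2 and T3 (section 5.3), so a gene main effect is the carrier minus non-carrier difference in disability averaged over all visits, one of them before randomisation.

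Two errors could follow. Genes that mark sicker children could be reported as predictors of CBT response. Genes that do alter response could be dropped at the p<0.1 screen, before any model that might show it. A larger sample does not help with the first error: it makes the severity association more certain.

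**Working it through.** **Inputs.** From 10.4: SD 4, planned treatment difference 1.5 points, 112 evaluable per group (224 in all). Assumed, because the documents give no figure: between-visit correlation 0.5, carrier share q = 0.20, complete data, and either all 224 or only 112 children genotyped.

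**1. The plan's own figure.** A two-sided t test with non-centrality r√n = 0.27 × √112 = 2.86 has 80.9% power, and the smallest correlation detectable at 80% is 0.267. So r = 0.27 reproduces, but for gene against disability. The detectable difference between arms in standardised gene slope is (1.96 + 0.84) × 2/√N, which is 0.37 at N = 224 and 0.53 at N = 112.

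**2. What the gene coefficient estimates.** Let a gene shift disability by L at every visit and change the CBT effect by D at T2 and T3. With complete data and equal correlations, the gene term is the carrier difference in the three-visit mean.
- Arms pooled: L + D × (2/3) × (1/2) = L + D/3.
- WebMAP only: L + 2D/3.

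**3. Standard errors.**
- Variance of the three-visit mean: 16 × (1 + 2 × 0.5)/3 = 10.67. Pooling without arm adds 0.25, because the arms differ by 1.5 × 2/3 = 1.0 point in the mean and 1.0² × ¼ = 0.25. The total is 10.92.
- Gene term, pooled: √[10.92/(Nq(1−q))] = √(10.92/35.84) = 0.552 at N = 224, and 0.781 at N = 112.
- Gene term, WebMAP only (112 children): √(10.67/17.92) = 0.772.
- Gene-by-arm on the T2/T3 mean adjusted for T1: the variance is 16 × 1.5/2 = 12, less 8²/16 = 4 explained by T1, leaving 8. SE = √[8 × (2/22.4 + 2/89.6)] = 0.945 at N = 224, and 1.336 at N = 112.

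**4. Chance of p < 0.05.** Simulated values, with the normal approximation Φ(effect/SE − 1.96) in brackets (lower tail added where it matters):

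| Gene | Analysed | As written | Gene-by-arm |
|---|---|---|---|
| Severity only, L = 1.5 | 224 pooled | 77% (78%) | 5% |
| Severity only, L = 1.5 | WebMAP only, 112 | 50% (49%) | not estimable |
| Severity only, L = 1.5 | 112 pooled | 49% (48%) | 5% |
| Response only, D = 1.5 | 224 pooled | 16% (15%) | 36% (35%) |
| Response only, D = 1.5 | 112 pooled | 9% (10%) | 20% (20%) |
| Response only, D = 3 | 224 pooled | 43% (44%) | 87% (89%) |
| Response only, D = 3 | 112 pooled | 23% (25%) | 59% (61%) |

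For a severity-only gene the true gene-by-arm effect is zero, so 5% is the nominal error rate.

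**5. The screen.** With critical value 1.645 and N = 224, a response-only gene with D = 1.5 (coefficient 0.5) passes p<0.1 with probability Φ(0.5/0.552 − 1.645) plus a small lower tail, about 23%. With D = 3 it passes about 55% of the time. The severity-only gene passes about 86%.

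**6. Other inputs.** With N = 224, carrier share 0.25 to 0.50 and correlation 0.5 to 0.7, a severity-only gene of 2 points is significant as written in 94–99% of trials (70–89% in WebMAP only), against about 5% for gene-by-arm-by-time. A response-only gene of 1.5 points is found in 14–20% as written and 27–54% by the interaction.

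**The case against.** The strongest reply is that silence is not exclusion. The covariate sentence says what the covariates include, which is not a closed list. The sentence before it gives treatment response as the purpose, and Hypothesis 2 names both arms and promises a stratified analysis. A reader might infer that the plan deliberately leaves arm out; the documents do not support that. What stands is narrower: the response term is not specified, while the screen, the selection step and the power statement are all written for the main effect.

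A second reply is that a WebMAP-only analysis was meant, since 112 in 10.4 is the size of one arm. Arm would then be absent by design, and the response share rises to two thirds. Without gene-by-time, however, the coefficient is still an average level, and the severity gene is still flagged in 50% of trials. Without controls, prognostic and predictive genes cannot be separated even with that term.

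A reader might also infer that the gene coefficient says nothing about response. That is too strong, because a third or two thirds of the response effect leaks in.

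Nor should 87% be read as the power of the repaired analysis. It needs a 3-point interaction, twice the whole planned treatment effect, and every completer genotyped. Sections 5.3 and 14.1 say that community participants outside INSPPIRE 2 have no genetic data, and 10.4 warns that power may fall for this reason. At 1.5 points both analyses mostly miss. The false labelling of severity genes is the firmer half of the point.

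**Conclusion.** The point holds: followed as written, the Aim 2 analysis answers a different question from Aim 2. It can present a severity gene as a response gene in roughly half to three quarters of trials under the section 4 assumptions (49–77%), against 5% for a gene-by-arm test. It finds a response-only gene about half as often as that test, or less (16% against 36% at 1.5 points, 43% against 87% at 3 points, with 224 genotyped).

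The percentages depend on assumed carrier share, correlation and genotyped number. The mixing of severity with a diluted response effect does not; it follows from the listed terms and the inclusion of T1. The exact one-third and two-thirds shares assume equal arms, complete data and the same response at T2 and T3. The Aim 1 model has its interaction, and its conclusion is not affected.

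**What to change.** In 14.1:
- State that Aim 2 uses both arms.
- Name the response term as the Aim 2 effect: either gene-by-arm on T2/T3 disability adjusted for T1, or gene-by-arm-by-time as an extension of the Aim 1 mixed model. Either is valid. At correlation 0.5 the baseline-adjusted form is more precise, because its residual variance is 8, against 12 + 16 − 2 × 8 = 12 for change from T1.
- Apply the p<0.1 screen and the multivariate/LASSO step to that term.
- Report gene main effects separately, labelled prognostic.
- Give the stratified analysis promised in Hypothesis 2 a model, or say that this is it.

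In 10.4, restate the Aim 2 power for the interaction in the genotyped INSPPIRE 2 subset, with an expected number and a range of carrier shares, since r = 0.27 describes the gene-disability correlation.

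Cost: wording and a new power calculation, with no new data. The stated Aim 2 power will look less favourable, and fewer genes will reach nominal significance.

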14.2. Quality control procedures for collected data:³²

The PI will supervise the study coordinator in collating and storing data and overseeing the integrity of study records. Data will be maintained on a network server with password protection and daily backup of data performed. The primary source of data will come from online assessments conducted on the REDCap website provided through ITHS at UW. REDCap has extensive security precautions appropriate for the storage of PHI. REDCap was developed specifically around HIPAA-Security guidelines and is recommended for use by researchers. In 2010 the Institute of Translational Health Sciences Biomedical Informatics Core (ITHS BMI) began supporting an installation of REDCap (Research Electronic Data Capture), which is software specifically designed for electronic data capture (EDC) for clinical trials. REDCap features include differentiated user roles and privileges, user authentication and authorization security, electronic signatures, SSL encryption, and comprehensive auditing to record and monitor access and data changes. PIs can configure REDCap User Rights and Data Access Groups to provide granular study data access to authorized study personnel. Access to servers is restricted to authorized ITHS BMI support personnel. The servers are located on ITHS-owned hardware in a secure server room at the University of Washington. This server room meets the technical requirements for HIPAA compliance and hosts other servers containing Protected Health Information (PHI). The Operating System of each server will be kept fully patched and firewalled in accordance with UW Medicine Information Security Policy. All identifying information will be removed from all electronic data, thus protecting the identities of participating families. Data will be kept for a minimum of seven years.

To ensure the accuracy of the data the following processes will be implemented:

- The study coordinator will check all data from REDCap questionnaires for completeness.
- REDCap will be exported directly to SPSS statistical software, to ensure the participant's responses are accurately entered into the database used for analyses. This will be secure and stored locally at Seattle Children's.

15. Confidentiality³³

15.1. Procedures to secure the data and/or specimens during storage, use, and transmission:

All participant data will be coded with a unique identification number, thus ensuring the subject's identity as a participant in this study will remain confidential. The research records will be kept confidential and protected health information will be safeguarded as required by Seattle Children's IRB and HIPAA regulations. The research staff and Seattle Children's IRB will be allowed to inspect the information collected from this study. Data collection online through REDCap will also be private and confidential. REDCap was developed specifically around HIPAA-Security guidelines and is recommended for use by researchers. In 2010 the Institute of Translational Health Sciences Biomedical Informatics Core (ITHS BMI) began supporting an installation of REDCap (Research Electronic Data

Capture), which is software specifically designed for electronic data capture (EDC) for clinical trials. REDCap features include differentiated user roles and privileges, user authentication and authorization security, electronic signatures, SSL encryption, and comprehensive auditing to record and monitor access and data changes. PIs can configure REDCap User Rights and Data Access Groups to provide granular study data access to authorized study personnel. Access to servers is restricted to authorized ITHS BMI support personnel. The servers are located on ITHS-owned hardware in a secure server room at the University of Washington. This server room meets the technical requirements for HIPAA compliance and hosts other servers containing Protected Health Information (PHI). The Operating System of each server will be kept fully patched and firewalled in accordance with UW Medicine Information Security Policy.

15.2. Location where the data and/or specimens will be stored:

All contact information and identifying data will be stored in a secure location within the PI's research lab

15.3. Length of time data and/or specimens will be stored:

Data will be kept for a minimum of seven years.

15.4. Individuals with access to data and/or specimens:

Only the research staff and Seattle Children's IRB will be allowed to inspect the information collected from this study

15.5. Process for the transmission of data and/or specimens outside Seattle Children's:

15.5.1. List of data and/or specimens that will be transmitted:

N/A

15.5.2. Individual(s) who will transmit data:

N/A

16. Provisions to Monitor Data to Ensure the Safety of Subjects³⁴

16.1. Plan to periodically evaluate the data collected regarding both harms and benefits to determine whether subjects remain safe:³⁵

N/A

16.2. Data reviewed to ensure safety of subjects:

N/A

16.3. Safety information collection procedures:

N/A

16.4. Frequency of cumulative data review:

N/A

16.5. Conditions that trigger an immediate suspension of the research:

N/A

17. Use of Social Media

17.1. Types of social media to be used and how:

Facebook, Instagram, Twitter, and LinkedIn will be used for recruitment purposes only - to share the study flyer information and provide a link to a REDCap community interest form where potential study participants can contact the study team if interested.

17.2. Measures in place to protect the privacy or confidentiality of subjects:³⁶

The only transmission of confidential information will occur via secure REDCap form. This will only happen when a community member is interested in the study and voluntarily discloses this information to the study team with the intention of being contacted about the study.

17.3. Types of communications that will be submitted to the IRB for review:³⁷

All study information included on social media websites will be copied from the IRB reviewed/approved study flyer. Advertisements for Facebook, Twitter and Instagram will be submitted to the IRB for their review.

17.4. If user-generated content will be active, how it will be monitored and what actions will be taken to ensure subject safety and study integrity:

N/A

18. Research Related Injury³⁸**18.1. Available compensation in the event of research related injury:**

N/A

19. Recruitment Methods³⁹**19.1. When, where, and how potential subjects will be recruited:**

Child participants with CP/ARP will be recruited from one of the 21 sites in the INSPPIRE cohort registry. Potential participants who are participating in the INSPPIRE 2 study and have consented to the sharing of their contact information for related research studies will be referred by their provider/research coordinator at their institution. Referring staff will send the potential participating family's contact information to the study team at Seattle Children's via secure email or REDCap form. The potential participant will be sent a letter and flyer describing the study, then if unresponsive, will be contacted over the phone/email/text by Seattle Children's to screen for eligibility and assess interest. We will contact participants up to 8 times in total, spread out over a period of 8 weeks. Participants will be given multiple opportunities to opt out of future contact, in their introductory letter and future contact attempts. Based on our prior experience recruiting from this population, this number of contact attempts is often necessary to make contact, even if patients have been referred by their provider after explicitly expressing interest. Fewer attempts would significantly reduce our chances of reaching a family. Furthermore, this study has potential to directly benefit patients. If participants are interested and eligible, consent forms will be emailed to participants and a consent call will be set up for a future time.

INSPPIRE2 participants who enroll in this study will be contacted to see if they would like to participate in a brief related follow-up study, STUDY00002765. This study consists of a single survey. See the STUDY00002765 protocol and related documents for further details about how these participants will be contacted. STUDY00002765 is conducted by the same PI and study team members.

Additional community participants will be identified via the websites and social media outlets (Facebook, Instagram, and Twitter) of pancreatitis patient advocacy groups such as the National Pancreas Foundation (NPF) and Mission Cure, through advertisements on Facebook

and Instagram, and through distribution of study flyers via interested gastroenterology clinics/providers. These participants will be able to view the study flyer, and if they are interested in participating, they may “self-refer” by filling out a secure REDCap form with their contact information and a few preliminary eligibility questions (see separate form). They may also call SCH staff directly if they have questions about the study. SCH staff will then contact these potential participants and screen them for eligibility over the phone/email/text. If eligible, consent forms will be emailed to participants and a consent call will be set up for a future time.

Additional potentially eligible participants will be identified from SCH clinic schedules and electronic medical records. Potential participants and their parents will receive an initial mailing with a letter informing them of potential study eligibility and giving them the option to decline contact. This letter will also include a flyer outlining study details. All potential participants will be approached two weeks after mailing the letter with a phone call, email, or text message from study staff inviting them to participate, screening for eligibility criteria, and completing the consent process for participants who agree to participate. Study staff will attempt to contact potential participants a total of three times over the phone, email, and/or text message.

